### 5.3 Process outcomes:

These will be recorded in a subset of sites and women via clinical audit.

- Number of women presenting with decreased fetal movements
- Interval between perceiving decreased fetal movements and presenting to hospital

## 6 Statistical Methods Section from the Protocol

### “ 8.2 Proposed Analysis

*For the binary outcomes being addressed in research questions Q1-Q4, data will be analysed by generalized linear mixed model with a random effect for hospital group and fixed effects for the intervention implementation and study time period. Data will be analysed on an intention to treat basis (the design of the trial means it is not possible to determine individual patient /caregiver compliance with the intervention). There will be no imputations for missing data. Subgroup analyses will include those with and without congenital anomalies. No interim analyses will be performed other than those requested by the trial steering committee, who will be the only group to view the interim analyses. A full statistical analysis plan will be developed and signed off prior to locking of the study database.*

*For research question Q5, the qualitative data will be audio recorded and transcribed. The data will be coded thematically and an analytical framework developed to make sense of patient experience of fetal movement and the intervention and also health care providers' perspectives and experiences. NVivo will be utilised to support the analysis. The RA and [name] will work together to ensure rigour and validity.*

*The process outcomes being assessed in Q6 (rates of induction of labour, number of women presenting with decreased fetal movements, interval between perceiving fetal movements and presenting to hospital) will be analysed using the same methods as for Q1-Q4, with the exception of the continuous outcome (interval between perceiving fetal movements and presenting to hospital) which will be analysed in a normal linear mixed model”.*

## **7 Overall Statistical Principles**

### **7.1 Data collection**

As per section 7 of the study protocol data will be collected from four different regions of the study.

Data will then be sent to the electronic Data Research and Innovation Service (eDRIS) National Safe Haven (NHS National Services Scotland) by Secure File Transfer Protocol (SFTP) (or other similar) for storage and subsequent analysis within a secure project area (the AFFIRM study database).

### **7.2 Data analysis**

The statistician at ECTU will perform the statistical programming and analysis to produce all summary tables and figures using the statistical packages SAS (v9.2 or a more recent version), IBM SPSS (version 19 or later) or R, whichever is the most appropriate to use in the National Safe Haven.

In general terms, categorical data will be presented using counts and percentages, whilst continuous variables will be presented using the mean, median, standard deviation (SD), minimum, maximum, inter quartile points at 25% and 75% (Q1 and Q3) and number of patients with an observation (n) in the statistical output,

All statistical tests will be 2-sided and will be performed using a 5% significance level, leading to 95% (2-sided) confidence intervals (CIs) and corresponding p-values, unless otherwise specified.

Distributional assumptions underlying the statistical analyses will be assessed by visual inspection of residual plots. Normality will be examined by normal probability plots. If the distributional assumptions for the parametric approach are not satisfied, further data transformation (for achieving Normality), or other suitable methods will be considered. This will be documented in the statistical results report together with the reasoning supporting the action taken, if applicable.

The Intent-to-treat (ITT) population will be used to summarise all data and all analyses unless otherwise specified.

For the main clinical paper, appropriate MS Word tables will be compiled using the statistical output generated at the National Safe Haven (Examples in Appendix 1)

### **7.3 Handling of missing data**

There will be no imputation for the data with regard to missing values or withdrawals in the statistical summaries and statistical analysis unless otherwise specified (see sensitivity analysis).

Where smoking status during pregnancy is missing, data will be imputed using the woman's smoking history at booking. Age at delivery (years) [1] will also be considered as a possible variable to inform the imputation.

### **7.4 Quality Control (QC) of Summary Tables and Statistical Analysis**

Suspected data errors identified in the database will be listed.

### **7.4.1 QC/Validation - Summary Tables**

A random selection of summary output table items will be QC'd using alternative methods (i.e. comparison of items in the table to results calculated by an alternative method).

### **7.4.2 QC/Validation - Statistical Analysis**

QC/Validation of statistical analyses will be performed by peer review of selected program codes, logs and outputs. Additionally, the primary outcomes analysis will be replicated independently by a second statistician.

### **7.5 Unblinding procedures**

The randomisation list is held at ECTU. This will be made available to the statistician performing the analysis within the National Safe Haven once all imported data have been received and a finalised copy of the statistical analysis plan has been signed off.

## **8 Population for Analysis**

### **8.1 Intent to treat population**

The intention-to-treat (ITT) population will include all babies of women delivering at one of the AFFIRM study maternity units for the duration of the study.

## **9 List of Analyses**

### **9.1 Recruitment and retention**

No formal statistical testing will be performed for recruitment and retention. A flow chart following the CONSORT [2] extension for cluster trials, adapted for stepped wedge designs will be provided. The statistical report will tabulate the number of centres recruited, randomised, completed and discontinued by intervention and overall. The number of women and babies included by study centre and geographical region will be presented.

### **9.2 Demographics, Clinical Characteristics**

No formal statistical testing will be performed for demographics and clinical characteristics. The following will be presented and summarised by intervention and overall:

Maternal parameters:

- Mother's age at delivery (years)
- Mother's height (cm)
- Mother's weight at booking (kg)
- Maternal BMI
- Ethnic group
- Smoker during pregnancy
- Smoking history at booking
- Deciles of deprivation (Scotland Only)
- Parity

- Number of births this pregnancy
- Mode of Delivery

### 9.3 Protocol deviations/violations

No formal statistical testing will be performed. All known protocol deviations/violations at centre level will be listed.

### 9.4 Compliance with allocated intervention by centre

This will measure how sites engaged with the intervention and will summarise whether the intervention was implemented; the timing of implementation versus the time point determined by the study randomisation; and the number of major protocol deviations by centre. The proportion of patients that fall within a compliant intervention period will be calculated by centre. Additionally, an “on treatment” variable will be calculated for which patients (women) will be grouped as active / control according to when the intervention was actually implemented in a site, instead of when it was randomised to have been implemented in that site. This variable will be used for a sensitivity analysis (see section 9.5.1)

### 9.5 Primary Outcome

The primary outcome will be summarised overall, and by study site and active/control periods expressed as a rate per 1000 live births. Number of stillbirths (CEMACH definition) will be analysed on an intention to treat basis, incorporating all patients in the ITT population for whom outcome data are available. The number of stillbirths will be compared before and after implementation of the Active intervention using a logistic regression generalised linear mixed model following the model structure described in Hussey and Hughes [3]. The effect of implementation of the Active intervention will be presented as an odds ratio and its 95% CI. The intervention groups will be ordered in such a way that an odds ratio of less than one corresponds to a benefit for Active Phase over Control Phase

The event rate  $\mu_{ij}$  in site  $i$ , study period  $j$  will be modelled in the linear component of the logistic regression as:

$$\mu + \alpha_i + \beta_j + \theta X_{ij}$$

where:  $\mu$  is the overall mean event rate on the logit scale;

$\alpha_i$  is a zero-mean random effect for site  $i$ ,  $\alpha_i \sim N(0, \tau^2)$ ;

$\beta_j$  is the fixed effect log-odds ratio for time period  $j$ , with  $\beta_1=0$  for identifiability;

$\theta$  is the fixed effect log-odds ratio for the intervention;

$X_{ij}$  is a (0/1) variable to indicate whether the intervention is implemented in site  $i$  during period  $j$ .

A site by intervention interaction random effect will be included in the model and retained if it is found to explain an important proportion of the variability in outcomes.

The patient-level covariate included will be maternal age and number of babies (one; more than one).

A secondary analysis adjusting for a full list of patient-level covariates will also be included (maternal age, parity, smoking status during pregnancy, maternal BMI, number of babies (one or more) and ethnicity). This will be performed as a complete-case analysis.

A further secondary analysis not adjusting for patient level covariates will also be performed.

Also, a Scotland only model will be generated with the patient-level covariates included in the primary analysis plus the deciles of deprivation.

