8 STATISTICS AND DATA ANALYSIS

8.1 SAMPLE SIZE CALCULATION

The sample size is the number of women delivering in hospitals participating in the study. Scotland has around 58,000 deliveries per year with 16 consultant led maternity units, 20 smaller units each delivering less than 350 babies per year, and seven units delivering less than five births per year (Appendix 2). The units involved in Perinatal Ireland (an all-Ireland research consortium across 7 academic centres in Ireland currently funded by the Health

Research Board, Ireland) have 50,000 births per year with seven large centres (Appendix 2). Combining one or two of the smaller units and one larger unit into a single “hospital group” for each local area could provide 24 hospital “groups” – the details of hospital groupings will be reviewed and finalised immediately prior to randomisation.

We calculated statistical power using the methodology for stepped wedge designs proposed in Hussey and Hughes (2007) (26). First, we analysed stillbirth event data from the Scottish Perinatal and Infant Mortality and Morbidity Report (SPIMMR) covering years 2005-2010 (4) to determine estimates of between- and within-unit variability in stillbirth rate. Analysis was by generalized linear mixed model for binary outcomes. The power calculation, as per equations (#7) and (#8) in (26) assumed: significance level 5%; analysis by generalized linear mixed model; deliveries equally distributed across hospital groupings; baseline stillbirth rate 0.438% (4); cluster coefficient of variation 0.333.

Finally, the statistical power depends on the number of groups in which the intervention is implemented at each stage of the stepped wedge design and the duration of recruitment at each “step”. Our study design proposes sequential introduction of the intervention into three hospital groups at a time at four month intervals over a 32 month period. This would give 92.4% power to detect a 30% relative risk reduction under the intervention and 80.7% power to detect a 25% reduction. A 30% risk reduction was seen in the Norwegian study; the anticipated effect sizes of 25% and 30% relative reduction take into account that the intervention will not have the power to reduce all stillbirths, since 20% of stillbirths in Ireland (5) and 15% in Scotland (4) are associated with congenital anomaly.

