8.2 PROPOSED ANALYSES

For the binary outcomes being addressed in research questions Q1-Q4, data will be analysed by generalized linear mixed model with a random effect for hospital group and fixed effects for the intervention implementation and study time period. Data will be analysed on an intention to treat basis (the design of the trial means it is not possible to determine individual patient /caregiver compliance with the intervention). There will be no imputations for missing data. Subgroup analyses will include those with and without congenital anomalies. No interim analyses will be performed other than those requested by the trial steering committee, who will be the only group to view the interim analyses. A full statistical analysis plan will be developed and signed off prior to locking of the study database.

For research question Q5, the qualitative data will be audio recorded and transcribed. The data will be coded thematically and an analytical framework developed to make sense of patient experience of fetal movement and the intervention and also health care providers’ perspectives and experiences. NVivo will be utilised to support the analysis. The RA and [name] will work together to ensure rigour and validity.

The process outcomes being assessed in Q6 (rates of induction of labour, number of women presenting with decreased fetal movements, interval between perceiving fetal movements and presenting to hospital) will be analysed using the same methods as for Q1-Q4, with the exception of the continuous outcome (interval between perceiving fetal movements and presenting to hospital) which will be analysed in a normal linear mixed model.

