## **9.6 Discrete Secondary Outcomes**

For the following binary outcome measures, we will use the same methods as for the primary outcome analysis which included adjustment for patient level covariates:

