**9.6.13 Rates of admission to the neonatal unit for term babies (those born at 37 weeks 0 days or greater)**

**9.6.14 Proportion of babies with fetal growth restriction**

**9.6.15 Rates of spontaneous vaginal delivery**

**9.6.16 Proportion of babies born preterm**

## **9.7 Continuous Secondary outcomes**

For the following continuous outcomes a mixed linear regression model will be used to compare the means between the intervention groups adjusting by a random effect for site and fixed effects for the intervention implementation and study time periods. The result will be presented as an adjusted difference in means together with its corresponding 95% CI and p-values:

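### The models for the common secondary outcomes have no site-by-period random effect, so if local rates drift their tests reject too often and their intervals are too narrow, by an amount the documents cannot fix

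*SAP*

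**What the plan says.** Protocol 8.2 plans, for the binary outcomes of Q1-Q4, a "generalized linear mixed model with a random effect for hospital group and fixed effects for the intervention implementation and study time period". SAP 9.5 writes the stillbirth model out as an overall mean, a normal random effect for site, a fixed effect for each study period and a fixed intervention effect, "following the model structure described in Hussey and Hughes [3". It adds a site-by-intervention random effect, retained only if it explains an important share of the variability; no threshold is given.

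SAP 9.6 applies this to the binary secondary outcomes: "we will use the same methods as for the primary outcome analysis". These include caesarean section, induction, elective delivery and neonatal admission. SAP 9.7 compares the continuous outcomes by a linear mixed model "adjusting by a random effect for site and fixed effects for the intervention implementation and study time periods", with no site-by-intervention term. SAP 7.2 sets the error rate: "All statistical tests will be 2-sided and will be performed using a 5% significance level".

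Neither document has a site-by-period term, a robust variance, a small-sample correction or a permutation test. The one time-related sensitivity analysis, in SAP 9.5.1, models how the intervention effect builds up or fades, which is a different component.

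**The concern.** The hypothesis of interest is that the package does not change the rate. The reference distribution is built under a narrower one: no effect, and each site's underlying rate moves only with the period effects that all sites share. If the site-by-intervention term is kept, one further shift per site is allowed, at its own crossover. A unit whose induction rate moves for local reasons within the control or the active phase breaks the narrower hypothesis but not the one of interest. The model then treats real local movement as information about the intervention and reports too small a standard error.

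This matters most where sampling noise is small, that is, for common outcomes in large cells. Secondary objectives Q2-Q4 (Protocol 2.1.2) concern caesarean section, induction, neonatal admission and undelivered growth restriction, which form the balance of harm and benefit. A change in one of these, in either direction, could be declared when the package did nothing.

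**Working it through.** **Inputs from the documents.** 24 hospital groups, three per step, eight steps (Protocol 8.1); nine four-month periods (SAP 3.2); a two-month washout (SAP 4.1); 58,000 + 50,000 deliveries a year (Protocol 8.1); stillbirth rate 0.438%; "cluster coefficient of variation 0.333"; "deliveries equally distributed across hospital groupings". Births per group-period: 108,000 × 3 / (24 × 9) = 1,500. Washout removes half a cell per group, leaving 216 − 12 = 204 cells, or 306,000 births, close to the 300,000 in Protocol 4.1.

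**The plan's own figure.** The Hussey-Hughes variance is I·σ²(σ² + T·τ²) / [(I·U − W)σ² + (U² + I·T·U − T·W − I·V)τ²].

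- I = 24, T = 9, U = 108, W = 1,836, V = 612
- σ² = 0.00438 × 0.99562 / 1,500 = 2.907×10⁻⁶
- τ² = (0.333 × 0.00438)² = 2.127×10⁻⁶
- Numerator: 24 × 2.907×10⁻⁶ × 22.05×10⁻⁶ = 1.539×10⁻⁹
- Denominator: 756σ² + 3,780τ² = 0.01024
- SE = 0.000388

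Power = Φ(0.00438 × reduction / SE − 1.96) = 92.4% for a 30% reduction and 80.6% for 25%; Protocol 8.1 states 92.4% and 80.7%. With washout the same method gives 88.2% and 74.6%, exactly as stated. The design inputs are therefore right.

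**Drift against sampling noise.** On the logit scale a cell's sampling variance is 1/[n·p(1−p)].

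- 25% outcome: 1/(1,500 × 0.1875) = 0.00356, SD 0.060. A drift SD of 0.05 to 0.10 (about 0.9 to 1.9 percentage points) adds variance 0.0025 to 0.01, or 0.7 to 2.8 times the sampling variance.
- Stillbirth: 1/(1,500 × 0.00438 × 0.99562) = 0.153, SD 0.39. A drift SD of 0.10 adds only 0.01/0.153 = 7%.

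**Rejection of a true null.** The drift SD and the common-outcome rates are assumptions. Setting: 24 × 9 cells, 1,500 births each, crossover cell halved, site SD 0.333 on the logit scale, independent drift, cell-level mixed models, 2,000 runs per row.

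| Outcome rate | Drift SD | Site intercept only, z | Site-by-intervention kept, z | Same, t on 22 df |
|---|---|---|---|---|
| 7% | 0.05 | 8.3% | 7.5% | 5.8% |
| 7% | 0.10 | 15.7% | 10.9% | 8.9% |
| 10% | 0.03 | 6.9% | 6.2% | 4.9% |
| 10% | 0.10 | 19.7% | 11.4% | 9.6% |
| 25% | 0.05 | 13.1% | 9.8% | 8.4% |
| 25% | 0.10 | 31.0% | 14.6% | 11.8% |
| 35% | 0.05 | 14.8% | 10.3% | 8.6% |
| 35% | 0.10 | 34.6% | 15.3% | 12.8% |
| 0.438% | 0 | 5.7% | 5.4% | 3.9% |
| 0.438% | 0.10 | 6.5% | 5.8% | 4.3% |

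For outcomes at 10% and 30% (1,000 runs, site SD 0.30), the kept-term model gives 4.7% and 5.4% at drift SD 0, and 18.4% and 19.2% at SD 0.20.

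**Cross-check.** For a 25% outcome with local movement of SD 1.4 points (logit SD about 0.014/0.1875 = 0.075), an intra-cluster correlation of 0.01 and 300,000 births, the true SE is 0.46 points. The models report 0.29 (intercept only) or 0.36 (term kept). Then 2[1 − Φ(1.96 × 0.29/0.46)] = 22% and 2[1 − Φ(1.96 × 0.36/0.46)] = 12.5%, against simulated 21.6% and 12.3% at SD 0.075. For scale, the worst-case rise in induction in Protocol Appendix 4 is 0.4-1% of women.

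**Persistent drift.** With first-order autocorrelation 0.7 and SD 0.05-0.20, the kept-term model rejects about 6-12% across the simulations run. A site intercept plus site-by-period term alone rejects about 8-12%.

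**After the change.** A site-by-period term alone gives about 5.5-6.8% (z) under independent drift. With both random terms the rate is about 5-6% under independent drift and 5-8% under autocorrelated drift. The smallest of these sets had 400 runs per setting (Monte Carlo error 1 to 2.4 points).

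**The case against.** The strongest reply is that the size rests on a quantity nobody has supplied. This stands. The documents give no site-by-period variance, no rates for induction or neonatal admission, and no statement of whether a z or t reference will be used. A reader might infer that the secondary tests have a false-positive rate of 9-15% as a matter of fact. They do not: that range belongs to a 25% outcome with drift SD 0.05-0.10, independent between periods, and a Wald z test. A t reference lowers the overall range at those SDs to about 6-13%.

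A reader might also infer that the protocol documents local drift. It does not. Its background surveys report variation between clinicians, Health Board investment is described as already made, and Protocol 5.5.2 ties control care to what was established before the study. Drift over 36 months is plausible, but it is an assumption. The likeliest kinds, such as a changed local policy, would persist, and for persistent drift the kept-term model does better, at about 6-12%.

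Third, the SAP models sites, whereas the simulation uses the protocol's 24 groups. With an illustrative 40 equal sites, one kept-term figure fell from 11% to 9%. Equal sizes and no patient covariates were assumed. No continuous outcome was simulated, so the intercept-only figures apply to 9.7 by analogy. Growth restriction undelivered at 40 weeks was not simulated separately.

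These points limit the size. They do not remove the omission, and the kept-term figures are the favourable case: 9.7 has no such term, and 9.6 may lose it under a rule without a threshold.

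**Conclusion.** The omission is real and worth correcting as a cheap improvement. With about 1,500 births per group-period, outcome rates of 7-35% and an assumed drift SD of 0.03-0.20, a nominal 5% Wald test rejects a true null about 6-19% of the time with the site-by-intervention term kept. With a site intercept only, which is 9.7 as written or 9.6 if the term is dropped, it rejects about 8-35% at SD 0.05-0.10. With no drift, both models are at about 5-6%.

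Because the model is printed in SAP 9.5, a reader might infer that the stillbirth result is unsound. The figures do not support that: with about 6.6 expected stillbirths per cell, sampling noise dominates, and at drift SD 0.10 or less the error with the term kept stays at about 5-6%. The point concerns the common secondary outcomes.

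**What to change.** In SAP 9.6.6-9.6.16 and 9.7, specify three zero-mean random effects: site, site-by-intervention and site-by-study-period. State that all three stay in the model whatever their estimated size. Both added terms are needed, because site-by-period alone does not hold the error under persistent drift. For 9.7 this means adding site-by-intervention as well.

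For the stillbirth and perinatal mortality outcomes (9.5 and 9.6.1-9.6.5), add the site-by-period term as a sensitivity analysis only, and report the change in the standard error. If a model does not converge, fit the same structure to site-by-period totals.

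The cost is SAP wording and one or two extra variance components, with no new data. Intervals for common outcomes widen: in the 25% example, adding a site-by-period term moves the reported SE from 0.29-0.36 to about 0.45 percentage points. Model fitting in the Safe Haven takes longer. The fallback to totals would also need the patient-level covariates entered as cell summaries or left out.
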